- 1) Receiving a physician diagnosis of COPD AND treatment for it (defined as receiving treatment at hospital or clinic for COPD)
- 2) Age \geq or = to 40 years

Exclusion criteria for patient participants are: Non- English speaking; cognitive dysfunction impairing ability to provide informed consent and follow instructions; active substance abuse or unstable psychiatric condition; terminal illness (i.e. less than 6 months life expectancy) that is non-COPD related; planning to move from area; living at a facility, such as Hospice or nursing home; unable to provide contact information.

Caregiver participant:

Inclusion Criteria: Invited by an enrolled patient participant to join them as caregiver (person involved in their healthcare); 18 yrs or older

Exclusion Criteria: Non-English speaking; Unable to provide contact information

6. Drugs/ Substances/ Devices

- a. The rationale for choosing the drug and dose or for choosing the device to be used. N/A
- b. Justification and safety information if FDA approved drugs will be administered for non-FDA approved indications or if doses or routes of administration or participant populations are changed. N/A
- c. Justification and safety information if non-FDA approved drugs without an IND will be administered. N/A

7. Study Statistics

- a. Primary outcome variable.

Change in Health-related Quality of Life at 6-month follow up compared to baseline, as measured by Total score on the St. George Respiratory Questionnaire.

b. Secondary outcome variables

Please see table below

Outcome	Baseline	3 months post	6 months post	9 months post	Measure/Instrument description
Patient Outcomes					
Age, Gender, Marital Status, Race/Ethnicity, Living alone Y/N	✓				
Spirometry : FEV1 % predicted and FEV1/FVC	✓				
Addiction to drugs or alcohol, mental health dx.	✓				CAGE questionnaire; Drug use coded diagnosis at the time of baseline assessment
Education, Income, Occupation	✓				
Health Literacy	✓				One item question on ease of filling of medical forms
mMRC Dyspnea Scale	✓	✓	✓	✓	One item
Medical hx. (Ht, Wt, previous PFTs, oral steroid use, class of inhaler treatments)	✓				Medical record
Number of hospitalizations in prior 1 year to enrollment	✓				Patient/Caregiver self-report
Time since last hospitalization (in mons)	✓				Patient/Caregiver self-report
No. of years since receiving COPD diagnosis	✓				Patient/Caregiver self-report
Smoking Status	✓	✓	✓	✓	Yes/No, pack-years Readiness to quit using 4 stages

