together, participated in a BREATHE call, or by having a phone conversation with their BREATHE pal containing discussion of COPD-related issues (determination based on BREATHE pal notes.) For a more detailed description of our complier-average causal effect analysis and IV approach, please refer to the statistical analysis plan in the supplemental study documents section (SAP_BREATHE2_2019Jun26).

The sample size calculation will be based on an overall comparison of the change between the baseline and 6-month measurements of the patients on the St. George scale (primary outcome) in the two arms (interaction term). The unadjusted per-arm sample size is based on a power of 0.80, alpha of 0.05, a minimally clinical significant difference in change scores of 4 points and a meta-analysis estimate of variability. The estimated sample size is 145 patients per arm, after accounting for a 15% attrition rate, assuming a within-patient correlation between measurements of 0.8.

Heterogeneity of Treatment Effects (HTE) HT-1

The goal of the HTE analyses in this study is to consider the difference in treatment effect between the two arms, taking into consideration differences in the arms that are not obviously accounted for in the balance created by the randomization scheme. Patient characteristics such as disease severity or caregivers' presence may show differences in the intervention's effect and thus are important avenues to explore for hypothesis generation. In this hypothesis generating HTE analysis, we will consider the following subgrouping variables: age (4 categories), gender, disease severity, baseline PAM score, and caregiver presence. Within the HCP PLUS Peer Support group, we will also consider subgrouping by the propensity for adherence to treatment.

HT-2, HT-3

Subgroup treatment effects will be estimated by including a three-way interaction between the subgroup variable, the study assignment variable, and the 6-month time variable in a generalized linear mixed RE model. We will test for a difference in treatment effect between subgroups by a hypothesis test of the overall three-way interaction in this model. We will report estimates of subgroup treatment effects with corresponding 95% confidence intervals (CIs). For a more detailed description of the heterogeneity of treatment effect, please refer to the statistical analysis plan in the supplemental study documents section (SAP_BREATHE2_2019Jun26).

- d. Early stopping rules.
No early stopping rules.

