adherent participants all those patients who experienced at least four or more encounters with their peer mentor. We will also conduct sensitivity analyses in the same manner as for the primary outcome.

Intervention Implementation Analysis

In addition to assessing the primary and secondary outcomes for patients we intend to investigate which patient characteristics determine participation in the HCP PLUS Peer Support. That is, we will investigate which patient characteristics are related to attendance at BREATHE get togethers, participation in BREATHE calls, and phone interactions with BREATHE pals. As in the CACE analysis, we will define overall participation in the HCP PLUS Peer Support group as experiencing at least 4 or more encounters with a peer mentor either by attending a get-together, participating in a BREATHE call, or having a phone conversation. We will define participation in group support via attendance at 4 or more BREATHE get togethers or BREATHE calls. We will define participation in individualized 1:1 support by 4 or more encounters with a BREATHE pals over the phone. We will use multivariable logistic regression to predict overall participation, as well as participation in group or 1:1 support , from baseline characteristics such as age, gender, education level, distance from patient's home to meeting location, oxygen use, whether patient lives alone, whether patient reports they have a caregiver, self-reported health status, PAM level, and baseline assessments of hope, support, anxiety and depression from Herth Hope Index and PROMIS measures.

Heterogeneity of Treatment Effect (HTE) (PCORI Standard HT-1, HT-2, and HT-3)

HT-1, HT-3:

The goal of the HTE analyses in this study is to consider the difference in treatment effect between the two groups, taking into consideration differences in the groups that are not obviously accounted for in the balance created by the randomization scheme. Patient characteristics such as disease severity or caregivers' presence may show differences in the intervention's effect and thus are important avenues to explore for hypothesis generation. In these hypothesis generating HTE analyses, we will consider the following subgrouping variables for the primary outcome of change in SGRQ from baseline to 6 months: age (4 categories),

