gender, disease severity (whether they are on continuous home oxygen), baseline PAM score (collapsed into low vs high levels), and caregiver presence (caregiver vs no caregiver). Within the HCP PLUS Peer Support group, we will also consider subgrouping by the propensity for adherence to treatment (collapsed into low vs high levels), with propensity for adherence to treatment as the estimated probability of adherence to treatment from our intervention implementation analysis described above.

HT-2, HT-3:

Subgroup treatment effects will be estimated by including a three-way interaction between the subgroup variable, the study assignment variable, and the 6-month time variable in a generalized linear mixed RE model. We will test for a difference in treatment effect between subgroups by a hypothesis test of the overall three-way interaction in this model. We will report estimates of subgroup treatment effects with corresponding 95% confidence intervals (CIs). For the comparison of propensity for adherence groups within the HCP PLUS Peer Support group, we will include an interaction between the subgroup variable and the 6-month time variable, test this interaction, and estimate subgroup effects with corresponding 95% CIs.

References

1. Jones PW. St George's Respiratory Questionnaire Manual. 2009;44(June):0-16.
3. PROMIS. Anxiety. A brief guide to the PROMIS Anxiety instruments. 2018:1-18.
4. PROMIS. Depression. A brief guide to the PROMIS Depression instruments. 2018:1-18.
5. PROMIS. Emotional Support. A brief guide to the PROMIS Emotional Support instruments. 2017:1-6.
6. PROMIS. Instrumental Support. A brief guide to the PROMIS Instrumental Support instruments. 2017:1-6.
7. PROMIS. Social Isolation. A brief guide to the PROMIS Social Isolation instruments.

2015:1-7.

8. PROMIS. Informational Support. A brief guide to the PROMIS Informational Support v2.0 instruments. 2015:1-7.

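### PAM and age are tested as effect modifiers in groups with unstated cut points; if modification is roughly linear, testing them on their continuous scales would recover some power in weak exploratory interaction tests

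*Combined protocol and SAP*

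**What the plan says.** The SAP section on heterogeneity of treatment effect lists the subgroup variables for the primary outcome. Age enters as "age (4 categories", PAM as "baseline PAM score (collapsed into low vs high levels", and severity as "disease severity (whether they are on continuous home oxygen"; gender and caregiver presence complete the list. Each modifier is tested by the overall three-way interaction of subgroup, arm and 6-month time, and subgroup effects are reported with 95% confidence intervals. Age in four categories therefore costs 3 degrees of freedom.

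The SAP gives no boundaries for the age bands, no PAM cut, and no analysis with a continuous modifier. Protocol section 7c also lists age in four categories but names the baseline PAM score without grouping it. Where PAM is an outcome (SAP, intermediate measure 9), it is analysed as a change in score. Both documents call these analyses hypothesis generating.

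**The concern.** Cutting a continuous modifier discards the differences between patients within each group. The trial is sized only for the main effect, so its interaction tests have little power to spare. If the effect of peer support changes gradually with activation or age, the planned coding is less likely to show it than a test on the original scale.

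The result also depends on where the cuts fall, and the plan does not say where. At stake is the sensitivity of an exploratory analysis; no confirmatory claim rests on it.

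**Working it through.** **Inputs.** Protocol section 7c: "The unadjusted per-arm sample size is based on a power of 0.80, alpha of 0.05". The target is a 4-point gap between arms in SGRQ change, with variability taken from a meta-analysis. The section also states that it is "assuming a within-patient correlation between measurements of 0.8", with 15% attrition and 145 patients per arm. The SAP reports 290 enrolled, 1:1. The documents give no SGRQ standard deviation and no sidedness for alpha; a two-sided test is assumed.

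**1. The plan's own figure.** With single-visit SD s and correlation 0.8, the change-score SD is s × √(2 × (1 − 0.8)) = 0.632s. Solving backwards, s ≈ 17.7 gives 11.2. Then n = 2 × (1.96 + 0.84)² × 11.2² / 4² ≈ 123 per arm, and 123 / 0.85 ≈ 145. The planned size is thus plausible but cannot be verified: other formulas reach about 145 with other SDs (about 18.6 with baseline adjustment; about 20, one-sided, gives 146). Evaluable patients: 2 × 123 = 246.

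**2. How weak the interaction tests are.** For two equal subgroups, the standard error of the difference in effects is twice that of the main effect. The main effect has 80% power at 4 points, so its standard error is 4 / 2.80 = 1.43 and the interaction's is 2.86. Power for a 4-point interaction is Φ(4 / 2.86 − 1.96), about 29%; 80% power needs 8 points. This follows from the design power and does not depend on the unstated SD.

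**3. Information kept after cutting.** For a normal modifier with a linear effect, a two-group cut at c with share p above it keeps φ(c)² / (p(1 − p)):

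- median split: 2/π = 64%, so 246 patients act like about 157;
- 30/70 split: 58%;
- 20/80 split: 49%;
- four equal bands (between-band variance): 86%.

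**4. Power.** Noncentral F on change scores, used as a stand-in for the mixed-model contrast. In scenario A the continuous test has 80% power (noncentrality 7.91). The split has 7.91 × 0.637 = 5.04 and the bands 7.91 × 0.861 = 6.81. In scenario B, low and high halves differ by 4 points. The slope is 4 / (2 × √(2/π)) = 2.51 points per SD of the modifier, and the noncentrality is 246 × 2.51² / (4 × 11.2²) ≈ 3.1.

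| Coding | A | B |
|---|---|---|
| Continuous, 1 df | 80% | 42% |
| Median split, 1 df | 61% | 29% |
| Four bands as a trend, 1 df | 74% | 37% |
| Four bands, overall 3 df | 57% | 24% |

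A simulation of 4,000 trials for scenario A gave 79%, 58% and 54% for the continuous, split and 3-df tests. For age, banding alone accounts for 80% to 74%; the rest of the fall, to 57%, comes from the 3-df test.

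**5. The reverse case.** If the effect steps by 8 points exactly at the median, the split has 80% power and the linear test 61%.

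**The case against.** Several points on the other side stand.

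- **The loss figures are conditional.** They need a normal modifier, a linear effect, and median or quartile cuts. The SAP specifies none of these, and its wording for PAM may mean grouping of existing levels.
- **The 80% starting point flatters the continuous test.** In scenario B it reaches only 42%. A reader might infer that grouping spoils an otherwise adequate test; the trial was never sized for interactions, and no coding makes it so.
- **Groups suit the stated output**, which is subgroup effects with confidence intervals. They also do better if the effect really steps at the cut.

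A further reading is tempting: that severity has been cut down to oxygen use although "Spirometry : FEV1 % predicted and FEV1/FVC" is collected at baseline, at a similar cost in power. The documents do not support that. Oxygen use is a separate variable, recorded in three levels in the protocol's outcomes table, and is not a cut of FEV1. Neither the prevalence of continuous use nor its relation to FEV1 is given, so no loss can be calculated. It is also tied to this intervention: mentors are matched partly on oxygen therapy, and one of the eight session themes is oxygen. It is a defensible modifier in its own right.

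These objections limit the point. They do not remove the case for testing PAM and age on their continuous scales beside the displayed groups.

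**Conclusion.** The point holds for PAM and age only, as a minor improvement. Under roughly linear modification, the planned coding costs about 19 percentage points of power for PAM and 23 for age when a continuous test would have 80%. In the 4-point scenario it costs about 13 and 18. These losses are illustrations under the stated distribution and cuts; the true loss cannot be computed without the cut points. Most of the loss for age comes from the 3-df test.

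A reader might infer that the primary result is weakened. It is not: the primary test does not use these groups, and the subgroup analyses are declared hypothesis generating.

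**What to change.** In the SAP's heterogeneity section, make the interaction tests arm × 6-month time × continuous PAM score and arm × 6-month time × continuous age, 1 df each. Keep the planned categories for displaying subgroup effects with 95% confidence intervals and for checking linearity, and state their cut points. If age must stay banded, a 1-df trend test across the bands would recover most of the loss.

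Keep continuous home oxygen as a planned modifier. Baseline FEV1 % predicted may be added as a further exploratory modifier beside it.

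The cost is SAP wording: no new data and no change to the primary analysis. The downside is the linearity assumption. The 1-df test does worse if the effect steps at the cut, and the displayed groups, being imprecise, give only a rough check.

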Peer support group conversations will be orchestrated at 8 'Get Together' events spanning a 6 months period. All participants who miss an event or were not interested/able to attend an event (based on preference, life circumstances, or health status), will be offered the option of attending a similarly themed 'BREATHE group call' to catch up on missed event conversations and their 'matched' BREATHE Pal will also contact him/her via phone to check in on them, answer any questions they have, and encourage them to attend the next Get together event. At end of these phone calls, the peer mentor has the option of talking about their call with the social worker. If a patient or a family caregiver expressed the need for additional healthcare or social support services, or if the peer mentor felt that they need it, they would inform the social worker who will facilitate the patient or family-caregiver access to these services.

At the group events (in person or group call), the group participants led by the BREATHE Pals will discuss COPD and its challenges, and share their experiences in coping with and managing it. See summary table below on general topics for discussion. The topics pertain to advancing patient understanding of COPD and its treatment options, introducing effective coping skills, and reinforcing a variety of positive behaviors including adherence to treatment plans, smoking cessation, joining pulmonary rehabilitation programs, and assuming an active, healthy lifestyle. The Breathe pals will use the COPD Patient Education guide and a set of commonly asked questions and answers (Commonly Asked Questions and Answers) as their content guide/reference for the group conversations and follow up phone conversations. Each meeting will include: 1) Education about COPD management strategies based on the themes in table below; 2) discussion of patient experiences and challenges related to using these strategies; and, 3) encouragement to set goals and problem solve challenges. The sessions will follow a sequence of themes from 1-8 and then repeat. A study participant may thus join the sessions sequence at any time point and continue for 8 sessions thus getting to participate in all 8 themes. If at any point the number of participants attending the sessions exceeded 20 people, the group will be split into two and new participants may join either group according to their preferred group meeting time.

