12. Participation in pulmonary rehabilitation at 3, 6, and 9 months post-enrollment.

Hypothesis: Patients receiving the HCP PLUS Peer Support will have greater level of participation in pulmonary rehabilitation than patients in the *HCP only* group.

13. Change in smoking status at 3, 6, and 9 months post-enrollment.

Hypothesis: Patients receiving the HCP PLUS Peer Support will have a higher smoking cessation rate than patients in the *HCP only* group.

Handling of Missing Data (PCORI [name]-4)

There are two types of missing data, at the respondent level (unit non-response) and at the specific question level (item non-response). At the respondent level, missing data occurred because of patient death, withdrawal from study, or inability to be reached via phone for an interview. Comparisons of missingness by several patient characteristics at baseline will be performed with Fisher's exact or Chi-Square tests to examine any potential systematic pattern to the missing data. For the specific case of the SGRQ instrument, values of 100 (the worst possible QoL score) will be imputed for any assessment in which a patient was not available because of death.

With respect to data at the specific question level, missing data will be handled according to each instrument collection manual. In some cases, for example the SGRQ,¹ PAM,² and PROMIS-anxiety,³ -depression,⁴ -emotional,⁵ and -instrumental support index⁶ score will be prepared in instrument specific calculators, provided by the instrument's authors, and accounted for any assignments of missing scores based on the availability of item responses. Missing data for other instruments such as PROMIS-social isolation⁷ and -informational support index⁸, understanding COPD⁹, and Morisky measure,¹⁰ will be handled according to the instrument's author's direction.

When no information is available for handling missing item responses on a particular instrument, a rule, allowing no more than 25% of the items for the scale/domain to be missing, was used. If less than 25% of the item responses were missing, the mean of the non-missing item responses

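### The propensity-for-adherence comparison is listed under heterogeneity of treatment effect but uses the peer arm alone, so its subgroup-by-6-month term mixes prognosis with effect modification

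*Combined protocol and SAP*

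**What the plan says.** The SAP (Heterogeneity of Treatment Effect, HT-1/HT-3) sets out its purpose: "The goal of the HTE analyses in this study is to consider the difference in treatment effect between the two groups". It calls these analyses hypothesis generating and names change in SGRQ from baseline to 6 months as the outcome.

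Age, gender, disease severity, baseline PAM and caregiver presence are examined with a subgroup × assignment × 6-month term (HT-2/HT-3): "We will test for a difference in treatment effect between subgroups by a hypothesis test of the overall three-way interaction in this model".

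Propensity for adherence is handled apart: "Within the HCP PLUS Peer Support group, we will also consider subgrouping by the propensity for adherence to treatment", split into low and high. The model has no assignment term: "For the comparison of propensity for adherence groups within the HCP PLUS Peer Support group, we will include an interaction between the subgroup variable" and 6-month time. The SAP will then "test this interaction, and estimate subgroup effects with corresponding 95% CIs".

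Protocol 7.c gives the same restriction to the peer arm. The one-arm model and its output are described only in the SAP.

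The score is the predicted probability of at least 4 peer encounters, from a logistic regression on baseline characteristics (SAP, Intervention Implementation Analysis). The predictors include age, oxygen use, living alone, and "self-reported health status, PAM level, and baseline assessments of hope, support, anxiety and depression from Herth Hope Index and PROMIS measures".

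Under Handling of Missing Data, for the SGRQ, "values of 100 (the worst possible QoL score) will be imputed for any assessment in which a patient was not available because of death".

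**The concern.** The section's question is whether the benefit of adding peer support differs between kinds of patient. A comparison made wholly inside the peer arm has no reference for how the same kinds of patient would have changed without peer support. If likely adherers would have done better or worse on the SGRQ anyway, that difference appears in full as the subgroup effect.

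A reader who finds it reported next to five genuine effect-modification tests could conclude that patients likely to adhere benefit more, when the data may show only that they have a different prognosis. The error can also run the other way: an opposing prognostic gap can hide real effect modification.

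**Working it through.** **1. What each term estimates.** Write A(s, arm) for mean 6-month change in propensity group s (high or low), and T(s) = A(s, peer) − A(s, HCP) for the treatment effect in that group.

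- One-arm term: A(high, peer) − A(low, peer) = [A(high, HCP) − A(low, HCP)] + [T(high) − T(low)], that is, prognostic difference plus effect modification.
- Three-way term: the one-arm term minus the same contrast in the HCP arm = T(high) − T(low), effect modification alone.

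This needs no assumed figure. With effect modification of −4 and a prognostic gap of +4, the one-arm term is 0 and the three-way term is −4.

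**2. A scale for illustration.** The plan states no figure for this analysis. Protocol 7.c gives 145 per arm, 15% attrition, power 0.80, alpha 0.05 (taken as two-sided), a 4-point difference and within-patient correlation 0.8. The SD is not given as a number, so 145 cannot be reproduced independently, only back-solved:

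- Evaluable per arm: 145 × 0.85 = 123.
- SD of change: 4 × √(123/2) / (1.96 + 0.84) = 11.2.
- Cross-sectional SD: 11.2 / √(2 × (1 − 0.8)) = 17.7.
- Residual SD after baseline adjustment: 17.7 × √(1 − 0.8²) = 10.6.

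**3. One-arm test, no treatment effect, halves of 62 and 61.** The SE is 10.6 × √(1/62 + 1/61) = 1.92 adjusted for baseline, or 2.02 unadjusted. Rejection rates from the noncentral t, at assumed prognostic gaps:

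| Assumed gap (points) | Adjusted | Unadjusted |
|---|---|---|
| 1 | 8% | 8% |
| 2 | 18% | 17% |
| 3 | 34% | 31% |

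At zero gap the one-arm test holds its 5%. In a simulation of 5,000 trials per case (unadjusted, the same −4 effect in both halves, gaps of 0, 2, 4 and 6), the one-arm estimate tracked the gap. The three-way estimate stayed near 0, with 4–5% rejection.

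**4. Deaths scored 100.** Assume deaths of 4% in one half and 2% in the other, mean baseline SGRQ of 40 to 60, and no mean change in survivors. The spurious gap is (0.04 − 0.02) × (100 − baseline): 0.02 × 40 = 0.8 to 0.02 × 60 = 1.2 points. Step 3 shows that a gap of about 1 point raises rejection only slightly above nominal.

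**5. Price of the three-way term.** Its SE is √2 times the one-arm SE: 2.71 adjusted, 2.86 unadjusted. Power for a 4-point difference between halves is 31% or 29%. For 80% power the difference must be 2.8 × SE, or 7.6 to 8.0 points.

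**The case against.** The strongest reply is that the SAP already sets this comparison apart. It keeps the phrase about treatment effects for the three-way model, says openly that the propensity comparison is within the peer arm, drops the word treatment when describing its output, says only that it will be considered, and labels the section hypothesis generating. That stands in part: no claim of effect modification is actually made. But nothing in the section says that the comparison is not a treatment-effect contrast, and its placement under the stated goal invites that reading.

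A second reply is that adherence is not defined in the HCP arm. Observed adherence is not, but the predicted probability uses baseline characteristics and can be computed for anyone who has them.

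A third is that every magnitude above rests on assumed gaps or death rates and a back-solved SD. That stands: the figures show scale only.

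A reader might go further and infer that likely adherers are healthier, so that the bias must favour peer support. The documents do not support a direction. Protocol section 4 does recognise patients "not interested/able to attend an event (based on preference, life circumstances, or health status"), but it offers them group calls and phone contact, and both count as encounters in the adherence definition.

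**Conclusion.** The point holds as a minor one. As written, the SAP's one-arm term cannot answer the HTE section's own question, because it estimates prognosis and effect modification together. That conclusion is algebraic. The size of the problem is unknown: about 8, 18 or 34% rejection for gaps of 1, 2 or 3 points, and a gap of about 0.8–1.2 points from 4% against 2% deaths, are conditional on 123 evaluable per arm, equal halves, no treatment effect and the assumed inputs.

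Two stronger readings should be resisted. The primary result is not affected: the intention-to-treat group × 6-month test does not use the propensity score. Nor does the protocol itself specify the one-arm model; section 7.c supports only the restriction to the peer arm.

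**What to change.** Preferred: fit the adherence model in the peer arm, apply it to baseline data in both arms, fix one low/high cut-point in advance, and test propensity × group × 6-month time as for the other subgroups. Use cross-fitted scores in the peer arm, so that a patient's own participation does not help determine that patient's score; HCP-arm scores are out of sample already.

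At the least: move the one-arm comparison out of the HTE section and state that it shows prognosis and treatment effect combined, not effect modification. This costs a sentence or two and is enough to prevent the misreading.

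The preferred route costs SAP wording and a little code. The SAP (Data Collection for Phase 2) has all participants interviewed before randomisation, so most predictors should exist in both arms. The exception is distance from home to the meeting place. It is a named predictor but is not listed among the patient baseline measures. Deriving it for HCP-arm patients, for example to their own study site, is an assumption; if it cannot be done, drop distance from the score.

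The downside is precision. With an SE of about 2.7–2.9 points and about 29–31% power for a 4-point difference, the three-way result stays exploratory and should be read from its confidence interval.
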